**UNIVERSIDADE FEDERAL DE SANTA CATARINA
CAMPUS ARARANGUÁ-ARA**

[name]
[contact] / [name]

RESEARCH PROJECT

Dry Needling and Photobiomodulation in the treatment of Myofascial Pain

Study Principal Investigator: [name] [name].

ABSTRACT

Myofascial Pain is a clinical condition of myalgic pain characterized mainly by the presence of Myofascial Trigger Points. Trigger points can be active or latent and they are described as a hypersensitive spot within a taut band in the muscle. The use of a computer for long periods has been shown as a trigger the trigger points. Dry Needling and Low-Level Laser Therapy (LLLT) has been described as good resources to treat myofascial pain. The hypothesis is that the association of the purposed interventions will have greater effects than only the dry needling intervention. The objective is to evaluate the effects of the dry needling and the laser in the treatment of upper trapezius trigger point on women. This study is composed of an evaluation and an intervention proposal with dry needling and LLLT to treat myofascial trigger points. The sample will be composed of 60 women, with 18 to 65 years old, divided into three groups. Twenty individuals will be in group Dry-On that will receive dry needling intervention on the trigger point, followed by LLLT intervention on. Twenty individuals will be in group Dry-Off that will receive dry needling intervention on the trigger point, followed by LLLT intervention turned off. Twenty individuals will be in group Control that will receive dry needling intervention at 1.5 cm from the trigger point, followed by LLLT intervention turned off. All interventions will be performed in one session. Outcome measures for pain, pressure pain threshold, functionality, and muscle activity will be collected.

Key-words: Myofascial pain; Pressure Pain Threshold; Low-Level Laser Therapy; Dry needling;

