These effects can be explained on the red light spectrum, near to infrared (660nm-905nm), have good effects to reduce inflammation, relieve pain, and accelerate the tissue regeneration (22). According to Gerwin (4), 2010, the LLLT has level B of the recommendation of probable effect on the treatment of pain caused by myofascial trigger points. Gattie et al (23), 2017, in their systematic review, state that the current information on dry needling intervention, whether compared to placebo treatment or when compared to another intervention, has very low to moderate quality of evidence. Furthermore, although the trigger points demonstrate changes in muscle activation obtained through electromyography (EMG), there are few studies that present EMG findings in order to demonstrate the effects of dry needling directly on muscle activity (24,25)

In this context, the present study aims to answer if the association of dry needling and photobiomodulation will have a greater effect on the treatment of myofascial trigger points than the dry needling alone or the placebo treatment.

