2.2. Specific Objectives

To evaluate the pain level before, during, and after the dry needling and photobiomodulation applications on the trigger point.

To identify the pain pressure threshold before and after dry needling and photobiomodulation applications on the trigger point

To verify the electromyographic activity of upper trapezius before and after the proposed treatments

To compare the effects fond intra and inter-groups for the applications of dry needling, dry needling and photobiomodulation, and control protocol.

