3.3.1. Inclusion Criteria

- Presence of active trigger point in upper trapezius.
- Use of computer for typing activities for, at least, 20 hours per week.
- Presence of mechanic pain in cervical region for less than three months.
- Pain level higher than 3 and lower than 8 on the Visual Analogue Scale (VAS) for neck and cervical regions in the last 30 days.

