The Visual Analogue Scale (VAS) will be used so the subjects can graduate their pain in shoulder and neck regions. The VAS level of pain will be acquired before the intervention (baseline), soon after the intervention (T₁), 30 minutes after the intervention (T₂), one week (T₃) and one month (T₄) after the intervention.

Pressure algometry will be used to evaluate the pain pressure threshold (PPT). This measured will be obtained before the intervention (baseline), soon after the intervention (T₁), and 30 minutes after the intervention (T₂). The equipment will be positioned on the trigger point mark and the subject will be instructed to report when the sensation changes from pressure to pain (16). The force measured in kilograms per square centimeter (kg / cm²) will correspond to

the quantity of pressure needed so the subject report change in pressure pain sensation (14). The pressure will increase constantly on 1 kg / cm² / s. It will be collected three measured, with an interval of 20 seconds between each measure, and the average of the three values will be used in data analysis.

The Neck Disability Index (NDI) is a unidimensional questionnaire composed of 10 items that have the aim to evaluate the limitation caused by pain and disability on the neck (30). This questionnaire is organized according to the type of activity performed and express positive levels of functional capability. Its score ranges from 0 to 50, where 0 to 4 is considered total capacity, 5 to 14 is mild incapacity, 15 to 24 is moderate incapacity, 25 to 34 is serious incapacity, and >35 is severe incapacity. The questionnaire will be self-applied and the subject will answer it before the intervention, one week and one month after intervention.

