3.6. Statistical Analysis

Data analysis will be performed through the GraphPad Prism[®] software, version 6.01 (GraphPad Software, La Jolla, California, USA). The Shapiro-Wilk test will be run to verify sample normality distribution. The Two-Way ANOVA test will be used for comparative analysis inter and intra-groups. The P value ($p < 0.05$) will be used to establish the significance of the results, in addition to the 95% Confidence Interval (95% CI). The values will be described as a mean \pm standard deviation.

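### The two-way ANOVA in Section 3.6 uses baseline at most as a level of time; adjusting for it as a covariate would estimate On minus Off more precisely from data already collected

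*Combined protocol and SAP*

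**What the plan says.** Section 3.6 gives one analysis method: "The Two-Way ANOVA test will be used for comparative analysis inter and intra-groups". It adds that a P value below 0.05 "will be used to establish the significance of the results, in addition to the 95% Confidence Interval (95% CI"). It does not name the two factors, say whether measurements are matched within woman, name a covariate, or say which difference the interval is for.

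The Abstract states the hypothesis: "The hypothesis is that the association of the purposed interventions will have greater effects than only the dry needling intervention". That is On versus Off. The Introduction asks a wider question, whether the combination has a "greater effect on the treatment of myofascial trigger points than the dry needling alone or the placebo treatment". Section 2.2 sets the objective "To compare the effects fond intra and inter-groups for the applications of dry needling, dry needling and photobiomodulation, and control protocol".

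Baseline is collected throughout. In Section 3.4, "The VAS level of pain will be acquired before the intervention (baseline), soon after the intervention (T₁"), then at 30 minutes, one week and one month. Pressure pain threshold (PPT) is taken at baseline and at two later times. For the Neck Disability Index (NDI), "the subject will answer it before the intervention, one week and one month after intervention". Section 2.2 has EMG measured before and after treatment.

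**The concern.** The measurement schedule makes group by time the natural reading of the two-way ANOVA. On that reading a woman's baseline is one more repeated response. The On-Off estimate at a visit is then either a difference in change from baseline, which carries the full noise of the baseline measurement, or a difference in post-treatment values, which ignores baseline. Adjusting for baseline as a covariate gives it the weight that the data support.

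Precision is at stake, not bias. Section 3.3 calls the 20 women per group a convenience sample and gives no power calculation, so there is no known reserve of precision. Section 3.6 also leaves open which difference gets the 95% CI, so the reported interval is not tied to the hypothesis in the Abstract.

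**Working it through.** **Inputs from the documents.** Three arms of 20, 60 in total (Section 3.3); significance level 0.05 (Section 3.6); VAS at baseline and four later times (Section 3.4). No SD, effect size, power or correlation is given, so the plan has no figure to reproduce beyond 3 × 20 = 60.

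**Assumptions.** Two-sided test; SD of 1 at each time; correlation r between baseline and follow-up, and equal between all times in the five-visit case; no losses; true On-Off difference of 0.8 SD (0.5 SD as a second case).

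**Step 1: standard error of On minus Off at one visit.** SE = √(k × 2/20), where k = 1 for the post-treatment value alone, 2(1 − r) for change from baseline, and 1 − r² with baseline as covariate. At r = 0.5, k is 1, 1 and 0.75, and the SE is 0.316, 0.316 and 0.274 SD. The ratio of covariate to change-score variance is (1 − r²)/[2(1 − r)] = (1 + r)/2, or 0.65, 0.75 and 0.85 at r = 0.3, 0.5 and 0.7.

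**Step 2: power at 0.8 SD.** Error degrees of freedom are 60 − 3 = 57 at a single visit, 56 with the covariate, and 57 × 4 = 228 for the matched five-visit ANOVA. The covariate figures come from simulation and include the small cost of estimating the slope.

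| r | Covariate | Change, single visit | Change, five-visit ANOVA error | Post-treatment only |
|---|---|---|---|---|
| 0.1 | 70% | 46% | 47% | 70% |
| 0.3 | 73-74% | 56% | 57% | 70% |
| 0.5 | 81% | 70% | 71% | 70% |
| 0.7 | 93% | 89-90% | 90% | 70% |

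At 0.5 SD, for r = 0.1/0.3/0.5/0.7, power is 34/37/43/58% with the covariate, 21/26/34/52% with the single-visit change score, and 34-35% post-treatment only. Simulated type I error is 4.9-5.2% for all three single-visit methods.

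**Step 3: interval width.** Mean 95% CI half-width in SD, for r = 0.1/0.3/0.5/0.7: covariate 0.63/0.61/0.55/0.45; change 0.85/0.75/0.63/0.49; post-treatment only 0.63.

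**Step 4: the VAS entry limits.** Section 3.3.1 requires "Pain level higher than 3 and lower than 8 on the Visual Analogue Scale (VAS"), which may lower r for VAS. As an extreme case, let the limits truncate baseline VAS itself, with assumed mean 5.5 and SD 2. The cut is then at ±2.5/2 = ±1.25 SD, and the baseline SD falls to u = 0.65 of its value. The restricted correlation is ru/√(1 − r² + r²u²), so r = 0.3/0.5/0.7 becomes 0.20/0.35/0.54. Power at 0.8 of the restricted post-treatment SD is then 71/75/83% (covariate), 63/70/81% (change) and 70% (post-treatment only). With an assumed SD of 1.5 to 2.5, r = 0.5 becomes 0.42 to 0.30. The limits apply to pain over the previous 30 days, so the real effect on r is probably smaller.

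**The case against.** The strongest reply is that this is a preference. The ANOVA is a recognised method, r is unknown, and over a post-treatment comparison at 0.8 SD the covariate gains nothing at r = 0.1 and about 4 points at r = 0.3. The large gaps are against a change score, which Section 3.6 does not name. The uncertainty about size stands. The objection to the benchmark does not: the change contrast computed with the five-visit ANOVA's own error term (47/57/71/90%) is also below the covariate analysis (70/73/81/93%) at every r tried.

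Three stronger readings are tempting, and the documents do not support them.

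- A reader might infer that a significant ANOVA will be reported as a laser effect. A three-arm test can reject because of needle site alone. With On equal to Off, r = 0.5, five VAS times and a constant needling effect of 0.3/0.5/0.8 SD, the simulated interaction is significant in 13/30/74% of runs. That is power against a real needling effect, not an error. The Introduction and Section 2.2 imply that groups will be compared with one another, so the figures only illustrate why such a test should not be read as a laser effect.
- A reader might infer that the planned analysis is biased. It is not, provided it is matched within woman, which Section 3.6 does not say. Run unmatched, the group test had a simulated type I error of 27/36/45% at r = 0.3/0.5/0.7.
- A reader might infer that On minus Off must be the only confirmatory test. The Introduction also names placebo as a comparator, so that choice is the sponsor's.

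**Conclusion.** The point holds as one of efficiency. On the group-by-time reading, and with matching within woman, the plan gives a valid On-Off contrast that is less precise than the data allow. At 0.8 SD and r = 0.3 to 0.7, the covariate adds roughly 3 to 17 percentage points of power over a change contrast and 3 to 23 over the post-treatment value alone. In the cases computed it is never materially worse than either.

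The size rests on assumed correlations and effects. Over a post-treatment comparison the gain is near zero at r = 0.1, and for VAS it may be small. It is worth making because baseline is already collected, but nothing here invalidates the trial.

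One further figure should not be counted here. Testing On-Off at all four post-treatment VAS visits with no laser effect gives at least one significant result in about 13-18% of runs, whichever of the three analyses is used. That belongs to the separate matter of there being no primary outcome or time point.

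**What to change.** Reword Section 3.6 as follows.

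- For each outcome, model post-treatment values with group as factor and the woman's own baseline as covariate. If visits are modelled jointly, include baseline by time and account for within-woman correlation.
- Report On minus Off from that model, with its 95% CI, as the estimate that answers the Abstract's hypothesis.
- Report On minus Control alongside it, because the Introduction also names placebo. The sponsor should set the order of the two, or an adjustment for both, before the data are seen.
- State that a significant three-arm or interaction test is not in itself evidence of a laser effect.

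No new data are needed. With no losses the cost is one degree of freedom at a single visit (57 to 56), or one per visit in a joint model (four for VAS). One item is open: check that the software version named in Section 3.6 fits such a model, and name other software if it does not.

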3. METHODS

3.1. Study Design

The present study is characterized as a randomized clinical trial, controlled, with a proposal of evaluation and intervention of dry needling associated to the low-level laser therapy (LLLT) to treat the trigger point caused by myofascial pain. The subjects will be randomized into three groups:

- Group On: application of dry needling and LLLT turned on directly on the trigger point;
- Group Off: application of dry needling and LLLT turned off directly on the trigger point;
- Placebo/Control group: application of dry needling and LLLT turned off away from the trigger point.

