3.3. Subjects

Women, with age between 18 and 65 years old, students, workers, and professors at Universidade Federal de Santa Catarina (UFSC) will be invited to participate in the research.

The invitation of subjects to participate in the study will be done through digital and printed folders that will be delivered at UFSC and on the social media. Those subjects that show interest to participate will be forwarded to an evaluation selection where it will be identified if the participant fits the inclusion criteria and where the Consent Form will be presented.

The sample will be composed by 20 subjects in each group, a total of 60 subjects, according to a convenience sample based on review studies of Cagnie et al., 2015(26), and Espejo-Antúnez et al., 2017 (12).

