3.5. Intervention Protocols

3.5.1. Dry needling protocol

The Dry Needling (DN) protocol will be performed in one session. It will be used acupuncture needles, individually packaged and sterilized, with 0.25 mm of thickness and 0.40 mm of length. Before the intervention, the skin will be clean with 70% alcohol. The therapist, then, will perform the grip in upper trapezius on the site of one of the two previously marked locations, according to the subject group allocation, and will insert the needle in the skin with help of a guide tube and will deepen the needle approximately 10 to 15 mm inside the trigger point (31).

The needle will be moved up and down as in the “fast-in and fast-out” technique described by Hong (18). The movement will be repeated during 30 seconds in a cadence of approximately 1 Hz (31). Once the study of Perreault, Dunning & Butts (32), in 2017, demonstrated that there is no need to seek the local twitch response to the DN have an effect, we do not have the aim to seek such response to the stimulus. The protocol will be the same for the groups that will receive the application directly on the trigger point and for the group that will receive the application away from the trigger point.

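### Section 3.6 names only a two-way ANOVA for VAS and NDI readings that run to one month after one session, and gives no rule for a missed reading; run as repeated measures, it would discard same-day VAS already collected.

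*Combined protocol and SAP*

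**What the plan says.** Treatment is given once (section 3.5.1): "The Dry Needling (DN) protocol will be performed in one session". Section 3.4 sets the readings. VAS is taken at baseline and then "soon after the intervention (T₁), 30 minutes after the intervention (T₂), one week (T₃) and one month (T₄) after the intervention". For NDI, "the subject will answer it before the intervention, one week and one month after intervention". Pressure pain threshold (PPT) stops at T2, 30 minutes after treatment.

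Section 3.3 fixes the size: "The sample will be composed by 20 subjects in each group, a total of 60 subjects". It calls this a convenience sample and gives no allowance for loss.

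Section 3.6 gives the whole analysis of these outcomes in one sentence: "The Two-Way ANOVA test will be used for comparative analysis inter and intra-groups". It does not name the two factors or say whether time is a repeated measure. It defines no analysis set and does not say what happens when a reading is missing. No other section does so.

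**The concern.** Baseline, T1 and T2 are taken around the session, so they could be available for all 60 women. T3, T4 and both NDI follow-ups depend on a response a week or a month later, with no further treatment to keep women in contact. The two ways of running the named test treat a missed late reading differently, and neither does it well.

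- **Repeated measures (time within woman).** The classical analysis needs every time level for each woman. If T3 or T4 is missing, her whole VAS row goes, including T1 and T2. If one NDI follow-up is missing, the other goes with it.
- **Ordinary two-way.** All her readings stay, but repeated readings on one woman are treated as if they came from different women, and the means at successive times no longer describe the same women.

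At stake are the precision of the same-day comparison of On with Off, which differ only in whether the laser is switched on, and in some circumstances its size, because it would rest on women selected after randomisation.

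**Working it through.** **Inputs from the documents.** One session; five VAS readings, two of them late; three NDI readings, two of them late; 20 women per arm, and 3 × 20 = 60 agrees with the stated total. The documents give no SD, correlation, effect size or loss rate. Every such value below is an assumption.

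**1. Complete rows left.** If each of two late readings is missed independently with probability m, the expected number of complete rows per arm is 20(1 − m)².
- m = 5%: 20 × 0.9025 = 18.1
- m = 10%: 20 × 0.81 = 16.2
- m = 20%: 20 × 0.64 = 12.8

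**2. Precision of same-day VAS.** If k of 20 rows per arm are dropped, the standard error is multiplied by √(20/(20 − k)).
- k = 2: √(20/18) = 1.054, up 5%
- k = 4: √(20/16) = 1.118, up 12%
- k = 6: √(20/14) = 1.195, up 20%

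Going from 20 to 16 per arm lowers the power to detect 0.8 SD (two-sided 5%, normal approximation) from 0.72 to 0.62. None of this needs any link between pain and return.

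**3. Ordinary two-way version.** Take a correlation of 0.6 between readings and write σ² for the variance of one reading. The mean of five readings on one woman has variance (1 + 4 × 0.6)/5 = 0.68σ², but independence implies σ²/5 = 0.20σ². The standard error of a group difference averaged over time is therefore too small by a factor of √(0.68/0.20) = 1.84. A change within a woman has variance 2(1 − 0.6)σ² = 0.8σ² against an implied 2σ², so its standard error is too large by √(2/0.8) = 1.58.

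**4. Bias with complete rows, same return rule in both arms.** Large-sample simulation: VAS SD 2, correlation 0.6 between all readings, true On-Off difference 1.0 at every reading after treatment, 20% average loss, and the log-odds of non-return linear in T2 pain.

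| Slope per VAS point | Raw difference at T2 | Change from baseline at T2 |
|---|---|---|
| 1 | 0.76 | 0.90 |
| 0.5 | 0.89 | 0.95 |
| 0.25 | 0.96 | 0.98 |

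At slope 1 the arms lose about 15% and 25%. The raw T4 difference is about 0.86, while the change-from-baseline contrast at T4 is about 1.00. The two contrasts differ because the retained women show a baseline imbalance of about −0.14. Reversing the sign of the slope (recovered women leave) gives much the same figures. With no true difference the bias is 0.00.

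**5. Bias when the return rule differs between arms.** In a second simulation (20 women per arm, same SD and correlation), pain was related to return in opposite directions in the two arms. With no true difference, complete rows gave +0.81 at T2 and +0.50 at T4. A likelihood model on all readings gave 0.02 and 0.03.

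**6. Limit of the likelihood model.** When return depends on the unseen one-month pain and the true difference is −1.5, the likelihood model gives −1.41 at T4 against −1.33 from complete rows. That is better, but not right.

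**The case against.** A reader might infer that the plan deletes women who miss a reading. The documents do not say so: section 3.6 never uses the term repeated measures, and an ordinary two-way ANOVA would keep the readings. This stands. The deletion is a consequence of the natural reading, not a stated rule.

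A reader might also infer that pain-dependent return by itself biases On against Off. It does not. With a common return rule and no true difference, only precision is lost.

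The larger bias figures also need steep selection. A slope of 1 per point at SD 2 is an odds ratio of e² ≈ 7.4 per SD of pain. An SD of 2 may be high at baseline, since entry pain must lie between 3 and 8 (a uniform spread over that range has SD 5/√12 = 1.44). Even the largest tabulated bias, 1.0 − 0.76 = 0.24, is well below the standard error of 2 × √(2/20) = 0.63 at 20 per arm. A group-by-time interaction concerns change from baseline, where the bias is smaller still. All of this stands.

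Loss may be low. The women are students and staff of the university that runs the laboratory, NDI is self-completed, and nothing says that the late readings need a visit. This is fair, and the loss rates above are assumptions for that reason.

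Finally, the likelihood model recovers the truth almost exactly when missingness is generated from observed T2 pain, but that follows from how the data were simulated. Step 6 shows the limit.

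What the objection does not remove is that the named test has no satisfactory way to treat a missed late reading, in either version, and that no other section supplies one.

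**Conclusion.** The point holds as a weakness of the stated method for VAS and NDI, and should be changed before the data are analysed. The firm cost of the complete-row version is precision: a same-day VAS standard error 5%, 12% or 20% wider if 2, 4 or 6 of 20 women per arm are lost, whatever the reason for the loss.

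Bias is conditional. It needs pain-dependent return together with arms that differ in pain or in how pain relates to return. Under a common rule and the assumed inputs it is modest and towards no effect. If the rule differs by arm, a difference can appear where none exists, but nothing in the documents suggests that it will.

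The loss of same-day readings after treatment concerns VAS only. NDI has no such reading, and PPT, which ends at T2, is untouched by missed returns. It would be wrong to extend the point to every outcome.

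**What to change.** In section 3.6, replace the two-way ANOVA for VAS and NDI with a linear mixed model: group, time and group-by-time, with correlation between readings within a woman. Fit it to every available reading of all randomised women in their allocated group. A missed T3 or T4 then removes only that reading. If the software named in 3.6 cannot fit the model, name one that can.

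At minimum, analyse T1 and T2 separately from T3 and T4, so that a missed late reading cannot remove same-day data.

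Report the number of missing readings by arm and time. Add a sensitivity analysis in which return depends on unseen pain, because the mixed model assumes that readings are missing at random given those observed.

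The cost is wording in 3.6, possibly different software, and one added analysis. No extra women, visits or measurements are needed. The reliance on missing-at-random is a small downside, and the sensitivity analysis addresses it.

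### If the two-way ANOVA pools one within-woman error over VAS readings minutes to a month apart, its group-by-time test and change intervals are probably miscalibrated, by an amount the documents do not fix

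*Combined protocol and SAP*

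**What the plan says.** The whole model statement in section 3.6 (Statistical Analysis) is: "The Two-Way ANOVA test will be used for comparative analysis inter and intra-groups". The section adds a normality test, a 0.05 significance level, 95% confidence intervals and the software ("Data analysis will be performed through the GraphPad Prism", version 6.01). It does not say whether the ANOVA is repeated-measures or ordinary. It names no subject term, sphericity check, epsilon correction or covariance structure, and it does not say which error the confidence intervals use.

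Section 3.4 (Evaluation procedures) sets the VAS schedule: "The VAS level of pain will be acquired before the intervention (baseline), soon after the intervention", then at 30 minutes, at one week, and finally "one month (T₄) after the intervention". That is three readings in one session and two much later.

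No other outcome has a stated schedule of this kind. Pressure pain threshold is a same-day measure ("This measured will be obtained before the intervention (baseline), soon after the intervention", then at 30 minutes). The Neck Disability Index has no same-day pair ("the subject will answer it before the intervention, one week and one month after intervention"). This point therefore concerns VAS only. Section 3.3 plans 20 women in each of three groups.

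**The concern.** A group-by-time ANOVA with time as a within-woman factor estimates one residual variance and uses it for every change over time. This is correct only under sphericity, meaning that the difference between any two readings has the same variance. With some readings minutes apart and others a week or a month apart, equal variances would be a coincidence.

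Two things follow if sphericity fails. The uncorrected F tests for time and group-by-time reject too often. Intervals for particular changes are also miscalibrated: too wide where the change varies less than average, too narrow where it varies more. The trial asks whether needling plus laser does better than needling alone. With 20 women per group, errors in the precision of On minus Off matter at both ends of the schedule.

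**Working it through.** **Inputs from the documents.** n = 20 per group, G = 3 groups, k = 5 VAS readings, two-sided 5% level (sidedness assumed). No variance figure is given that could be reproduced. All SDs and correlations below are assumptions.

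**Formulas (time within woman).**
- Pooled error: MSE = mean variance − mean covariance over the 10 pairs of readings, with df = 3 × 19 × 4 = 228.
- Pooled half-width for On minus Off in change from baseline: t(228) × √(4·MSE/n), with t = 1.970.
- Correct half-width: t(57) × √(2·V/n), where V = Vj + V0 − 2·C0j is the variance of that change and t = 2.002.

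The ratio of the two half-widths is the same for a within-group change.

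**One case in full.** Take SD 1.8 cm throughout, with correlations 0.8 same-day, 0.4 same-day to later and 0.6 between one week and one month.
- Mean correlation = (3 × 0.8 + 6 × 0.4 + 1 × 0.6)/10 = 0.54, so MSE = 3.24 × 0.46 = 1.49.
- Pooled half-width = 1.970 × √(4 × 1.49/20) = about 1.07 cm.
- Same-day: V = 2 × 3.24 × 0.2 = 1.296; correct half-width = 2.002 × √(2 × 1.296/20) = 0.72 cm. The pooled interval is about 1.49 times too wide.
- One month: V = 2 × 3.24 × 0.6 = 3.888; correct half-width = 2.002 × √(2 × 3.888/20) = 1.25 cm. The pooled interval is about 14% too narrow.
- In 20,000 simulated trials with no treatment effect, the group-by-time type I error was 7.9% and coverage was 99.6% same-day and 91.3% at one month.

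**Range at equal SDs.** Here the correlation between one week and one month is set to the cross-day value.

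| Same-day / cross-day correlation | Same-day width ratio (coverage) | One-month width ratio (coverage) |
|---|---|---|
| 0.9 / 0.5 | 1.92 (about 100%) | 0.86 (91.4%) |
| 0.8 / 0.4 | 1.52 (99.8%) | 0.88 (92.2%) |
| 0.7 / 0.5 | 1.19 (98.3%) | 0.92 (93.5%) |
| 0.7 / 0.6 | 1.09 (97.1%) | 0.95 (94.2%) |
| 0.6 / 0.6 | 0.98 (95.1%) | 0.98 (95.1%) |

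The last row is spherical. Its 0.98 reflects only the larger degrees of freedom (1.970/2.002). Simulated type I error with equal correlations and SDs was 5.0%, so the covariance pattern is the cause.

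**SDs rising over time.** With SDs from 1.5 to 2.1 and correlations 0.8/0.4/0.6, type I error was 8.3%. The pooled half-width was 1.09 against a correct 0.62 same-day (1.09/0.62 = 1.76) and 1.29 at one month (1.09/1.29 = 0.84, 16% too narrow, coverage 90.8%). With SDs from 1.3 to 2.4 and correlations 0.8/0.3/0.5, type I error was 8.8%. In the mild 0.7/0.5 case it was 5.7%.

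**Acute response to needling.** Treatment falls between baseline and the first post-treatment reading, which may weaken that correlation. Hold T1-T2 at 0.8, cross-day at 0.4, T3-T4 at 0.55 and SDs equal, and lower only the baseline-to-T1/T2 correlation. At 0.7, 0.6, 0.5 and 0.4 the same-day ratio is 1.25, 1.11, 1.01 and 0.94.

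**Ordinary two-way ANOVA (no subject term).** The error is the mean variance, with df = 285. Change intervals are then too wide at both ends: 1.3 to 4.4 times same-day and 1.17 to 1.55 times at one month, over the equal-SD patterns tried.

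**Patterns outside the quoted range.** Correlations 0.95/0.30 give 3.13 times same-day. A graded decay of 0.85/0.55/0.40 gives 0.81 at one month (89.7%). A baseline SD of 1.3 against 2.2 on the day and 2.0 later, with correlations 0.6/0.4, gives 1.08 at one month, slightly too wide.

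**The case against.** The strongest objection is that a reader might infer too much: that same-day intervals are certainly far too wide and one-month intervals certainly too narrow. The documents do not support that. They never name a repeated-measures model, give no SD or correlation, and do not say that the confidence intervals use the ANOVA error or that change from baseline is the contrast. Under an ordinary ANOVA the one-month direction reverses. Group differences at a single visit under that model, with equal SDs, would be unaffected (ratio 1.00).

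The idea that pain changes little over 30 minutes fits T1 to T2 better than baseline to T1, because needling comes in between. If women respond very differently to it, the same-day excess disappears or turns slightly negative, as shown above.

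The entry limits on pain do not settle the matter either. They refer to the preceding 30 days, not to the baseline VAS itself. If they narrow only the baseline spread (SD 1.3 against 2.0 later, correlations 0.8/0.4/0.55), the one-month interval is nearly right (ratio 0.96, coverage 94.7%).

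A reader might also infer a large loss of power. With a standard error of 0.345 cm, a true 1 cm same-day difference exceeds the correct threshold of 0.69 cm with probability 0.81 and the pooled threshold of 1.06 cm with probability 0.43. Those figures belong to one assumed covariance and one assumed effect, and are illustrative only.

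These points limit the certainty and size. They do not rescue the plan: neither reading of the ANOVA gives each VAS change its own error, and type I error stayed at about 6-9% in the clearly non-spherical repeated-measures cases, including those with a weakened baseline correlation.

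**Conclusion.** The point holds in conditional form. Section 3.6 does not state the error structure, and a single pooled within-woman error is poorly suited to this VAS schedule.

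On that reading, and over plausible assumed covariances:
- group-by-time type I error is about 6-9% instead of 5%, and close to nominal only when correlations and SDs are nearly equal;
- same-day change intervals are 0.94 to about 1.9 times the correct width, the direction depending on how variable the acute response to needling is;
- one-month change intervals are about 0-16% too narrow, with coverage of about 91-95%.

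Confidence is high for the mechanism and moderate for the size. The change is worth making because it is cheap and also settles which ANOVA is meant.

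**What to change.** In section 3.6, state that On minus Off will be estimated at each VAS reading with that reading's own error variance. Two routes do this:
- a separate between-group model at each post-treatment reading; or
- one mixed model with an unstructured covariance over the five readings and small-sample degrees of freedom (Kenward-Roger is one choice).

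If an ANOVA table is kept, say that time is a within-woman factor, apply the Greenhouse-Geisser correction to the time and group-by-time terms, and do not use its pooled error for comparisons at single readings.

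The cost is wording and a little more analysis work, with no extra women or visits. One-week and one-month intervals may become modestly wider, by about 0-20%. The documents do not say whether the named software fits the mixed model; the per-reading route does not depend on that.
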